#### 5.1.2. Secondary study endpoint

##### **Assessed at 3 and 6 months ( $\pm$ 1 month):**

- Functional outcome: defined as a score of 0–1 on the Modified Rankin Scale (mRS). The mRS ranges from 0 (no symptoms) to 6 (death). Lower scores reflect better functional recovery.
- Number of participants with major bleeding events: defined according to the criteria established by the International Society on Thrombosis and Haemostasis (ISTH) (see Appendix B)
- Number of participants with clinically relevant non-major bleeding (CRNMB) events: defined according to the criteria established by the International Society on Thrombosis and Haemostasis (ISTH) (see Appendix B)
- Number of participants with symptomatic recurrent VTE
- Health-related quality of life, measured by the EQ-5D-5L instrument and the Vietnamese population value set validated by Mai et al.
- Serial D-dimer measurements after CVT: plasma D-dimer levels will be measured at 3 and 6 months using a standardized quantitative assay. Values will be reported in ng/mL and interpreted in the context of post-CVT coagulation activity

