## **5.2. Study procedures**

Baseline clinical and radiological data, including patient demographics, risk factors, imaging findings, anticoagulant treatment details, and in-hospital events during the acute phase of CVT, will be collected for all enrolled patients.

Participants will be followed up at 3 and 6 months after diagnosis. Data collected at these time points will include:

- Type and duration of oral anticoagulant therapy
- Clinical events, including recurrent thrombotic or bleeding events
- Degree of disability will be assessed using mRS
- Venous recanalization will be assessed at 6 months using brain MRI with venography or CT venography. Recanalization will be categorized as complete, partial, or none, based on the classification proposed by Aguiar de Sousa et al
- Health-related quality of life, evaluated using the EQ-5D-5L instrument. This tool evaluates five domains (mobility, self-care, usual activities, pain/discomfort, and anxiety/depression), each with five levels of severity. A utility index score will be calculated using the Vietnamese EQ-5D-5L value set, ranging from -0.511 to 1.000, where 1.000 indicates perfect health, 0.000 corresponds to death, scores below 0 indicate health states considered worse than death by the general Vietnamese population.
- Presence of chronic headache, defined as a headache occurring on  $\geq 15$  days per month and persisting for more than 3 months following the acute CVT event, consistent with the International Classification of Headache Disorders, 3rd edition

(ICHD-3). Headache-related disability, assessed using the Headache Impact Test (HIT-6)

All data will be collected as part of routine clinical care during outpatient visits or structured telephone interviews and recorded using standardized case report forms.

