## **6. STATISTICAL ANALYSES**

All statistical analyses will be conducted using R software (version 4.4.1). Statistical significance will be set at a two-sided p-value < 0.05.

Descriptive statistics will be used to summarize baseline characteristics. Continuous variables will be reported as means  $\pm$  standard deviations (SD) or medians with interquartile ranges (IQR), depending on distribution. Categorical variables will be expressed as counts and percentages.

The primary endpoint: a composite of major bleeding (per ISTH criteria) or symptomatic recurrent venous thromboembolism (VTE), including cerebral venous thrombosis, deep vein thrombosis, pulmonary embolism, or splanchnic vein thrombosis—will be analyzed as a time-to-event outcome. Kaplan–Meier survival curves will be constructed, and group comparisons will be performed using the log-rank test. Cumulative event rates at 6 months will be reported with 95% confidence intervals.

For secondary endpoints, the following analyses will be conducted:

- Functional outcome (mRS 0-1 vs 2-6 at 3 and 6 months) will be analyzed using logistic regression to identify predictors of favorable recovery.

- Venous recanalization status at 6 months will be described as complete, partial, or absent, based on follow-up imaging, and summarized as proportions.
- Rates of major bleeding, any bleeding, symptomatic recurrent VTE, and arterial thrombotic events will be summarized descriptively and reported with 95% confidence intervals.
- Health-related quality of life (EQ-5D-5L), chronic post-CVT headache (HIT-6), at 3 and 6 months will be compared using paired t-tests or Wilcoxon signed-rank tests, as appropriate.
- Changes in D-dimer levels from baseline to follow-up will be analyzed using paired tests and visualized longitudinally.

Missing data will be handled using complete case analysis. If the missing rate exceeds 10% for any variable, sensitivity analyses will be performed.

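### Section 6 makes complete-case paired tests the main analysis of D-dimer, EQ-5D-5L and HIT-6, and its per-variable 10% trigger need not fire when up to 17% of pairs are lost

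*Protocol*

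**What the plan says.** Section 6 gives one missing-data method for all analyses: "Missing data will be handled using complete case analysis". A second rule follows: "If the missing rate exceeds 10% for any variable, sensitivity analyses will be performed". The section does not define a variable for this purpose.

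Three secondary outcomes are analysed as pairs. EQ-5D-5L and HIT-6 "at 3 and 6 months will be compared using paired t-tests or Wilcoxon signed-rank tests, as appropriate". For D-dimer, "Changes in D-dimer levels from baseline to follow-up will be analyzed using paired tests and visualized longitudinally". Recanalization at 6 months has no paired test; it is summarised as proportions.

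On data collection, Section 5.2 says "All data will be collected as part of routine clinical care during outpatient visits or structured telephone interviews". Section 5.1.2 says that "plasma D-dimer levels will be measured at 3 and 6 months using a standardized quantitative assay", and Section 5.2 requires MR or CT venography for recanalization. Section 8 expects items such as follow-up imaging to be unavailable in only a few patients. Section 5.3 sets minimum enrolment at 69.

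**The concern.** A paired test uses only patients with both values. For D-dimer, the plan's own follow-up procedure creates a route to missing values: a patient followed by telephone gives no plasma sample. Whether a pair exists then depends on clinic attendance, which may be related to how the patient is doing. If patients with high earlier values are the ones lost, the remaining patients start low, and regression to the mean shows up as change.

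The safeguard is a rate threshold applied to one variable at a time. A pair is lost when either value is missing, so each time point can stay under 10% while the analysis loses more than 10% of patients. At stake are the size and direction of the reported change in secondary outcomes. The primary endpoint is analysed by Kaplan–Meier and is not affected by this point.

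**Working it through.** **Inputs from the protocol.** N = 69 (Section 5.3); 10% threshold per variable, complete-case pairs and two-sided 0.05 (Section 6). Section 6 gives no missing rate, correlation or selection strength that could be reproduced, so those below are assumptions.

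**1. Where the trigger fires.** 6/69 = 8.7% does not exceed 10%; 7/69 = 10.1% does. One variable can therefore miss at most 6 values without firing.

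**2. Patients lost with 6 missing at each time point.**

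| Pattern | Two time points | Three time points |
|---|---|---|
| Same patients | 6 (8.7%) | 6 (8.7%) |
| Independent, 69 × [1 − (63/69)^v] | 11.5 (16.6%) | 16.5 (23.9%) |
| Different patients, 6v | 12 (17.4%) | 18 (26.1%) |

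The three-point column applies to any joint use of baseline, 3 and 6 months; each paired test uses two points. Applied to the analysis set, the same 10% rule would fire at 7 lost patients.

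**3. Precision.** By the noncentral t distribution, the standardised paired difference detectable with 80% power is 0.342 with 69 pairs, 0.378 with 57 and 0.400 with 51. Power at 0.342 falls from 80.0% to 71.9% and 66.9%.

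**4. Bias if loss depends on the earlier value.** Assume two standard normal values with correlation ρ, and a later value whose log-odds of being missing rise linearly with the earlier one (slope 0.7 to 1.0 per SD). If the earlier mean among retained patients lies δ below the mean of all patients, then

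bias in mean change = (1 − ρ) × δ.

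Averaging over the assumed logistic model gives δ of about 0.06 to 0.08 at 8.7% missing and 0.19 to 0.25 at 30% missing. For ρ from 0.7 to 0.3:

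- 8.7% missing: 0.3 × 0.06 = 0.02 SD to 0.7 × 0.08 = 0.06 SD.
- 30% missing: 0.3 × 0.19 = 0.06 SD to 0.7 × 0.25 = 0.18 SD.

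**5. Type I error under no true change.** At the worst corner (30% missing, ρ = 0.3, slope 1.0) the standard error is about √(2 × 0.7)/√(0.7 × 69) = 1.183/6.95 = 0.170. The bias is then 0.175/0.170 = 1.03 standard errors, and P(Z > 1.96 − 1.03) + P(Z < −1.96 − 1.03) is about 18%. Simulation over the whole grid gives about 5.5% to 6.4% with 6 of 69 missing and about 8% to 18% at 30% missing.

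**6. The alternative.** In the same simulations, maximum likelihood using every observed earlier value had bias near zero and similar variance to the paired estimate. The gain is in bias, not in precision.

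**The case against.** Most of the case on the other side stands, and it limits the point.

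- **Telephone follow-up does not threaten every paired outcome.** A reader might infer that it does. EQ-5D-5L and HIT-6 are questionnaires that can be asked by telephone, which should reduce their missingness. Recanalization needs imaging but has no paired test. Only D-dimer combines a paired test with a blood sample.
- **The large errors are not hidden by the trigger.** The 30% figures put all the loss on one variable, where the rule already demands sensitivity analyses. At the most one variable can lose silently, the error is close to nominal.
- **Type I error does not exceed 0.05 as a matter of course.** It does so only under selective loss, which is plausible for D-dimer but nowhere stated. No change is also a weak null for D-dimer measured from the acute phase. The bias formula does not need that null.
- **If the same patients miss both visits, the trigger works.** Telephone contact alone suggests that pattern. For D-dimer, however, Section 4.1 admits outpatient-clinic entries and referrals, so a baseline value could be missing in different patients from those followed by telephone.
- **A multivariable collapse is not shown.** With five variables each missing 6 values independently, 69 × (63/69)^5, about 44 patients, would remain. The protocol specifies no such model, and Section 8 acknowledges limited power for complex ones.
- **Baseline D-dimer is not omitted from the plan.** It is not named in the Section 5.2 baseline list, but that list is given as examples and Section 6 plans a change from baseline. This is drafting only.
- **The content of the sensitivity analyses may sit in an SAP.** That is why the point rests only on the method and trigger that Section 6 states.

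**Conclusion.** The point holds as a minor one. Complete-case pairing is a weaker default than an analysis of all observed values, and the case is clearest for D-dimer. The likely harm is small if missing data are as few as Section 8 expects, and material only if loss is both heavy and selective. The bias and error ranges rest on the assumed slope and correlation and on loss that depends on the earlier observed value.

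The trigger arithmetic needs no distributional assumption, but its upper figures require different patients to be missing at each time point. The correct statement is that the rule need not detect joint loss, not that it cannot. In addition, no threshold on a rate, per variable or per analysis, can show whether the loss is selective. That is the stronger reason to change the default analysis rather than the trigger alone.

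**What to change.** In Section 6:

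1. Analyse D-dimer (log scale), EQ-5D-5L and HIT-6 with a repeated-measures mixed model, with visit as a fixed effect and all observed values used. With two or three visits, an unstructured covariance is feasible. Keep the paired t or Wilcoxon test as a supportive analysis.
2. Apply the 10% trigger to the share of patients dropped from each analysis.
3. For recanalization, report the proportions with all missing scans counted as none, and again as complete. With m scans missing, the bounds for complete recanalization lie m/69 apart, for example 8.7 percentage points for 6.

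As a drafting matter, name D-dimer in the Section 5.2 baseline list.

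The cost is a few sentences of protocol text, standard R functions and a little more analysis work. The downside is that the model relies on missing-at-random and on approximate normality. Normality is least comfortable for the bounded EQ-5D-5L index, hence the retained Wilcoxon test. The model would not cure loss that depends on the unseen value.

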## **7. ETHICAL CONSIDERATIONS**

This study is a doctoral research project conducted as part of the PhD training program at Hanoi Medical University. The study was officially approved by the university on March 3, 2025, under Decision No. 580/QĐ-DHYHN.

Ethical approval was granted by the Ethics Committee of Bach Mai Hospital on July 4, 2025, under Decision No. 45/BM-HĐĐĐ. The study will be conducted in accordance with the principles of the Declaration of Helsinki (2013) and Good Clinical Practice (GCP) guidelines. The research will take place at Bach Mai Hospital, a national tertiary referral center for cerebrovascular diseases in Vietnam.

All eligible participants will be required to provide written informed consent before enrollment. Patients will be informed of the study's purpose, procedures, potential risks and benefits, their rights to confidentiality, and the option to withdraw from the study at any point without affecting their ongoing care.

This is a prospective, observational study. All interventions and follow-up procedures are part of standard clinical management for patients with cerebral venous thrombosis (CVT).

## **Study protocol: Treatment Outcomes of DOACs in CVT: A Prospective Study in Vietnam**

No experimental drugs or procedures will be introduced. Treatment decisions—including the use of direct oral anticoagulants—are made entirely by the attending physicians based on current guidelines and clinical judgment.

To protect privacy, personal data will be de-identified and stored on secure hospital servers with restricted access. Only aggregated, anonymized data will be used for publication or dissemination.

Any protocol deviations or serious adverse events observed during the study will be documented and reported to the Institutional Review Board (IRB) in accordance with national and institutional regulations.

### **8. LIMITATIONS**

This study has several limitations. First, it is a single-center investigation conducted at Bach Mai Hospital, a national tertiary referral center. While this may raise concerns regarding generalizability, the hospital receives the majority of CVT cases from a wide geographic area in northern Vietnam, including referrals from provincial and district-level hospitals. Therefore, the study population is expected to be broadly representative of the CVT patient population in real-world clinical practice within the region.

Second, given the rarity of CVT and the fixed 2-year enrollment window, the sample size is expected to be limited. This may reduce the statistical power to perform robust subgroup analyses or develop complex multivariable models. However, the study is designed to maximize data completeness through close follow-up and adherence to protocol-defined procedures.

Third, although the study currently includes both DOAC and VKA group, the planned analysis will primarily focus on the DOAC subgroup. This approach reflects the growing interest in the real-world effectiveness and safety of DOACs in CVT management. Including VKA patients in the recruitment phase may still provide useful contextual information for future comparative analyses.

Finally, some outcome data, such as follow-up imaging for venous recanalization or standardized cognitive assessments, may be unavailable for a small number of patients due to loss to follow-up or logistical constraints. Nonetheless, the study team is committed to minimizing missing data through proactive patient engagement and structured follow-up planning.

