## SUMMARY

**Rationale:** Cerebral venous thrombosis (CVT) is a rare condition. Once the diagnosis is established, current guidelines consistently recommend the early initiation of anticoagulation therapy with heparin, even in the presence of intracerebral hemorrhage. Upon clinical and radiological stabilization, treatment is typically transitioned to oral anticoagulants, including either vitamin K antagonists (VKA) or direct oral anticoagulants (DOACs). Since 2019, emerging evidence from randomized controlled trials such as RESPECT-CVT, CHOICE-CVT, and SECRET, along with large-scale international observational studies including ACTION-CVT and DOAC-CVT has demonstrated that DOACs can be safely used in the treatment of CVT. However, due to the rarity of the condition, most existing studies are limited by small sample sizes. Therefore, there is a growing need for additional studies across diverse geographic regions to expand the global evidence base on DOACs use in CVT. Such data will help enable more accurate assessment and analysis of treatment outcomes in patients with CVT receiving DOACs therapy.

**Objective:** To evaluate treatment outcomes of DOAC therapy in CVT patients.

**Study Design:** A prospective cohort study at Bach Mai Hospital, Vietnam, enrolling a minimum of 69 patients with CVT treated with DOACs.

**Study Population:** Adult patients ( $\geq 18$  years old) with radiologically confirmed CVT, treated with therapeutic-dose heparin in the acute phase and subsequently with a direct oral anticoagulant. All will be recruited from Bach Mai Hospital, the national referral center for CVT in northern Vietnam.

**Primary study endpoint:** the primary endpoint is a composite of the number of patients who experience either major bleeding, as defined by the International Society on Thrombosis and Haemostasis (ISTH), or a venous thromboembolic event (VTE) - including recurrent CVT, deep vein thrombosis of any limb, pulmonary embolism, or splanchnic vein thrombosis — within up to 6 months of follow-up.

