## 1. INTRODUCTION AND RATIONALE

CVT accounts for only 0.5-1% of all diagnosed and treated stroke cases worldwide. Previous studies have demonstrated that patients with CVT typically exhibit distinct clinical characteristics compared to those with other types of stroke. Notably, disproportionately affects younger individuals, with the majority of cases occurring in patients under 50 years of age and approximately two-thirds involving women. Clinically, CVT often presents with symptoms associated with elevated intracranial pressure or focal brain parenchymal lesions, which may or may not be associated with mass effect.

Current international guidelines uniformly recommend initiating treatment with low-molecular-weight heparin (LMWH) or unfractionated heparin during the acute phase. Once the clinical status and imaging findings have stabilized, oral anticoagulation is advised for a duration of 3-12 months, depending on the patient's individual risk profile.

In recent years, increasing attention has been directed toward the safety and efficacy of DOACs in the management of CVT. The first randomized controlled trial (RCT) evaluating DOAC use in CVT was the RESPECT-CVT trial, published in 2019, which assessed dabigatran. This was followed by CHOICE-CVT, was conducted in China. Both studies compared dabigatran with vitamin K antagonists (VKAs) and found no significant differences in safety and efficacy between the two groups. In 2023, the SECRET trial - an RCT comparing rivaroxaban with VKA - reported comparable outcomes. However, due to the rarity of CVT, all of these RCTs were limited by relatively small sample sizes, underscoring the inherent difficulty of conducting large-scale RCTs for rare conditions.

To complement these findings, large multicenter observational studies have been undertaken. Notably, the ACTION-CVT and DOAC-CVT studies have provided real-world evidence supporting the use of DOACs, demonstrating comparable safety and effectiveness to VKAs. DOACs also offer several practical advantages, including fixed dosing, fewer drug-food interactions, and no requirement for routine INR monitoring. Nevertheless, even these observational studies have not enrolled patient numbers in the thousands, thereby limiting the statistical power for robust subgroup analyses.

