## **Study protocol: Treatment Outcomes of DOACs in CVT: A Prospective Study in Vietnam**

Recent international guidelines now permit the use of either VKAs or DOACs in the treatment of CVT, acknowledging the growing body of evidence indicating similar safety and efficacy profiles. Research in this area remains ongoing worldwide.

In Vietnam, research on CVT treatment outcomes - particularly regarding the use of DOACs - is still limited. Moreover, due to the rarity of the condition and the complexity of evaluating multiple risk factors, patients with CVT are typically referred to major stroke centers for specialized management. Consequently, patient cohorts from such tertiary centers may provide insights that are representative of the national CVT population, rather than being confined to local or institutional patterns.

The primary objective of the present study, Treatment Outcomes of DOACs in CVT, is to evaluate the real-world safety and efficacy of DOACs in the management of CVT in Vietnam. The secondary objective is to assess clinical outcomes and identify factors associated with treatment response during follow-up.

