## 4. ELIGIBILITY CRITERIA

### 4.1. Population

All consecutive adult patients diagnosed with CVT at Bach Mai Hospital were considered eligible for inclusion. Patients could be enrolled during initial hospitalization or through the outpatient stroke clinic. Both newly diagnosed cases and those referred from other facilities for further management were included.

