### 4.2. Inclusion criteria

- Signed informed consent (ICF) to participate in the study
- Age  $\geq$  18 years
- Confirmed diagnosis of cerebral venous thrombosis (CVT) based on clinical presentation and neuroimaging, including one or more of the following:

MRI and MRV, AND/OR

CT and CTV, AND/OR

MRI or CT combined with DSA

- Initiation of DOACs within 5 to 15 days after starting treatment with heparin

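### Entry requires a DOAC start 5 to 15 days after heparin, so the cohort cannot stand for all CVT patients in the region, as Section 8 expects it to

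*Protocol*

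**What the plan says.** Four parts of the protocol bear on who the cohort represents.

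- **Source population (Section 4.1).** "All consecutive adult patients diagnosed with CVT at Bach Mai Hospital were considered eligible for inclusion". Enrolment may take place in hospital or through the outpatient stroke clinic, and includes referrals from other facilities.
- **Entry rule (Section 4.2).** "Initiation of DOACs within 5 to 15 days after starting treatment with heparin". The Summary describes the same population: "treated with therapeutic-dose heparin in the acute phase and subsequently with a direct oral anticoagulant".
- **Timing of the switch (Summary and Section 1).** The Summary says: "Upon clinical and radiological stabilization, treatment is typically transitioned to oral anticoagulants". Section 1 says of guideline advice: "Once the clinical status and imaging findings have stabilized, oral anticoagulation is advised".
- **Representativeness (Sections 8 and 1).** Section 8 concludes that "the study population is expected to be broadly representative of the CVT patient population in real-world clinical practice within the region". Section 1 says, more cautiously, that cohorts from tertiary centres "may provide insights that are representative of the national CVT population".

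Section 8 lists four limitations: single centre, small sample, focus on the DOAC subgroup, and missing outcome data. Within the third it says that VKA patients are also being recruited. Visit timing is fixed in Section 5.2: "Participants will be followed up at 3 and 6 months after diagnosis".

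**The concern.** Section 8 makes its claim about CVT patients, not about CVT patients who received a DOAC. Its only support is geography: the hospital draws cases from a wide area. Wide referral can answer a worry about local practice. It cannot undo an entry rule that depends on what happened to the patient after diagnosis.

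The rule requires the patient to be alive at the switch, and the attending physician to have chosen a DOAC and started it inside an 11-day window (days 5 to 15 inclusive). Those who die first are not a random part of the CVT population with respect to the outcomes reported here: all-cause mortality, mRS 0–1, and a primary composite that includes fatal bleeding under Appendix B. If the Section 8 statement is carried into the conclusions, readers may take the results as the outlook for CVT patients in northern Vietnam, when they describe patients who had already come through the period before the switch.

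**Working it through.** **No plan figure to reproduce.** The only design number is the minimum of 69 patients. Section 5.3 justifies it by rarity and the single-centre design and gives no inputs. The point does not depend on it. The check is mainly one of setting the text side by side.

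**Step 1. Who can enter**

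| Course after diagnosis | Section 4.1 | Section 4.2 |
|---|---|---|
| Dies before any DOAC | considered eligible | cannot enter |
| Alive, no DOAC by day 15 of heparin | considered eligible | cannot enter |
| DOAC started before day 5 of heparin | considered eligible | cannot enter |
| Given a VKA instead | considered eligible | cannot enter, although Section 8 says VKA patients are recruited |
| DOAC started on days 5 to 15 | considered eligible | can enter, subject to the other criteria |

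The first row is certain: a dead patient cannot start a DOAC. Enrolment from the outpatient clinic or after referral adds a further route that requires survival. Recruiting VKA patients would not bring early deaths back if the oral switch follows acute heparin for them too, as the Summary and Section 1 describe.

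**Step 2. Follow-up clock.** Visits are timed from diagnosis, while entry requires a later DOAC start. For everyone in the DOAC cohort, the time from diagnosis to the switch is therefore free of death by design.

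**Step 3. Direction for mortality.** Among all consecutive CVT patients let

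- d = share who die before a DOAC start,
- u = share alive but not entering, with 6-month mortality μ,
- m = 6-month mortality in those who enter.

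All-CVT mortality = d + uμ + (1 − d − u)m. This exceeds m when d(1 − m) > u(m − μ). With u = 0, any early death is enough. As an extreme offset, suppose u = 20% with no deaths at all (μ = 0) and m = 3%. Then d need only exceed 0.20 × 0.03 / 0.97 = 0.62%. Understatement is therefore likely, though not a logical certainty.

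**Step 4. Illustration of size.** All inputs are assumptions; none comes from the protocol.

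| d | u | μ | all-CVT mortality, m = 1% | all-CVT mortality, m = 3% |
|---|---|---|---|---|
| 1% | 0 | – | 0.01 + 0.99 × 0.01 = 1.99% | 0.01 + 0.99 × 0.03 = 3.97% |
| 3% | 10% | 10% | 0.03 + 0.01 + 0.87 × 0.01 = 4.87% | 0.03 + 0.01 + 0.87 × 0.03 = 6.61% |
| 5% | 20% | 20% | 0.05 + 0.04 + 0.75 × 0.01 = 9.75% | 0.05 + 0.04 + 0.75 × 0.03 = 11.25% |
| 10% | 0 | – | 0.10 + 0.90 × 0.01 = 10.9% | 0.10 + 0.90 × 0.03 = 12.7% |

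Ratios to m run from 3.97/3 = 1.3 to 10.9/1 = 10.9.

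**Step 5. Functional outcome.** Section 6 contrasts mRS 0–1 with 2–6, and 6 is death. Early deaths would count as unfavourable. If f is the share with mRS 0–1 among those who enter and u = 0, the share in all CVT is (1 − d)f, that is 0.99f to 0.90f for d = 1% to 10%.

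**Step 6. The confidence interval does not cover this.** One death in 69 is 1.4%, with exact 95% interval 0.0% to 7.8%. That interval reflects sampling error among enrolled patients and says nothing about deaths that could not be enrolled.

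**The case against.** The strongest reply is that the design matches its stated target. The objectives in the Summary and Section 2 concern CVT patients treated with DOACs, and requiring a DOAC start is how such a cohort is defined. No endpoint or analysis is stated for all CVT patients. This stands: the entry rule is legitimate, and the estimates for the population it defines are not invalidated. It does not rescue the Section 8 sentence, which carries no DOAC qualifier.

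It is also fair that the claims are hedged. Section 8 states an expectation in answer to the single-centre concern, and the national statement in Section 1 says only that tertiary cohorts may be informative. Section 8 does disclose the focus on the DOAC subgroup, but not the selection by survival to the switch.

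A reader might infer more than the text supports:

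- **That unstable patients, or those with a haemorrhage before the switch, cannot enter.** Stability is not a criterion in Sections 4.2 or 4.3; the Summary and Section 1 describe usual practice and guideline advice. No exclusion concerns intracranial bleeding or disability, and Section 5.2 records acute-phase in-hospital events. Such patients enter if a DOAC starts in the window and the other criteria are met.
- **That VKA patients are simply not recruited.** Section 8 says they are, in conflict with Section 4.2. The documents do not settle it.
- **That comparison with outside cohorts would favour DOACs.** Section 6 plans no external comparison, and the documents do not say how other studies counted follow-up.

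**Conclusion.** The concern holds in this form: Section 8 attributes to the cohort a property that the entry rule does not allow, and the limitations do not disclose the selection. It affects the stated target population, not the validity of estimates for patients who start a DOAC 5 to 15 days after heparin.

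That deaths before the switch are missing is certain from the text. That all-CVT mortality is understated is likely, and rests on early deaths not being outweighed by lower-risk patients among the other non-entrants. The size cannot be estimated from the protocol. It would be tempting to attach a fixed factor. For instance, 2% mortality in enrolled patients and 30% in the 5% to 20% who never enter give 0.95 × 2% + 0.05 × 30% = 3.4% and 0.80 × 2% + 0.20 × 30% = 7.6%, or 1.7 to 3.8 times. These inputs are as much assumed as those that gave 1.3 to 10.9, and the spread shows that no factor should be quoted as a finding.

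The point should be corrected, and preferably during recruitment, since early deaths are easier to log as they occur than to reconstruct later.

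**What to change.** 1. **Section 8.** Restrict the representativeness statement, and the conclusions drawn from the study, to CVT patients who survive to and start a DOAC 5 to 15 days after heparin. Add this selection as a named limitation.
2. **Section 1.** Qualify the national statement in the same way.
3. **Sections 4.1, 4.2 and 8.** Reconcile the description of all consecutive adults as eligible with the DOAC-start criterion, and reconcile the statement that VKA patients are recruited with that same criterion.
4. **Reporting.** Beside the mortality and primary results, give an aggregate, de-identified count of consecutive CVT patients not entered, by reason: death before DOAC start, DOAC outside the window, VKA, exclusion criterion, no consent. Section 7 requires written consent before enrolment, so the count should follow the ethics committee's rules on patients who have not consented.

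No eligibility or treatment rule needs to change for this point. The cost is a narrower stated conclusion, some wording, and a little logging of patients whom Section 4.1 already says are considered.
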